11.2 Disease Parameters

Measurable Disease

Bi-dimensionally, contrast-enhancing, measurable lesions with clearly defined margins by CT or MRI scan, with a minimal diameter of 1 cm, and visible on 2 axial slices (\geq 5 mm apart with 0 mm skip). Measurement of tumor around a cyst or surgical cavity, if necessary, requires a minimum thickness of 3 mm. If there are too many measurable lesions to measure at each evaluation, the investigator must choose the largest two to be followed before a participant is entered on study. The remaining lesions will be considered non-measureable for the purpose of objective response determination. Unless progression is observed, objective response can only be determined when all measurable and non-measurable lesions are assessed.

Non-Measurable Evaluable Disease

Unidimensionally measurable lesions, masses with margins not clearly defined, lesions with maximal diameter <1cm.

11.3 Response/Progression Categories

The RANO Response Criteria will be used in this study as summarized below.

11.3.1 Complete response (CR).

All of the following criteria must be met:

- a. Complete disappearance of all enhancing measurable and non-measurable disease sustained for at least 8 weeks. In the absence of a confirming scan at least 4 weeks later, this scan will be considered only stable disease.
- b. No new lesions.
- c. All measurable and non-measurable lesions must be assessed using the same techniques as baseline.
- d. Participants must be on no steroids or on physiologic replacement doses only.
- e. Stable or improved clinically, for clinical signs and symptoms present at baseline and recorded to be disease related.
- f. Stable or improved non-enhancing (T2/FLAIR) lesions.

Non-measurable disease cannot have a complete response.

11.3.2 Partial response (PR)

All of the following criteria must be met:

- a. Greater than or equal to 50% decrease compared to baseline in the sum of products of perpendicular diameters of all measurable enhancing lesions sustained for at least 8 weeks. In the absence of a confirming scan at least 4 weeks later, this scan will be considered only stable disease.
- b. No progression of non-measurable disease.
- c. No new lesions.
- d. All measurable and non-measurable lesions must be assessed using the same techniques as baseline.
- e. The steroid dose at the time of the scan evaluation should be no greater than the dose at time of baseline scan.
- f. Stable or improved non-enhancing (T2/FLAIR) lesions on same or lower dose of corticosteroids compared to baseline scan.
- g. Stable or improved, for clinical signs and symptoms present at baseline and recorded to be disease related clinically.

Non-measurable disease cannot have a partial response.

11.3.3 **Progressive disease (PD)**

Any of the following criterions must be met:

a. >25% increase in sum of the products of perpendicular diameters of enhancing

lesions (over best response or baseline if no decrease) on stable or increasing doses of corticosteroids and sustained for at least 8 weeks. In the absence of a confirming scan at least 4 weeks later, this scan will be considered only stable disease.

- b. Any new enhancing measurable lesion.
- c. Clear clinical deterioration not attributable to other causes apart from the tumor (e.g. seizures, medication side effects, complications of therapy, cerebrovascular events, infection, etc.). The definition of clinical deterioration is left to the discretion of the investigator, but it is recommended that a decline in the Karnofsky Performance Score (KPS) from 100 or 90 to 70 or less, a decline in KPS of at least 20 from 80 or less, or a decline in KPS from any baseline to 50 or less, for at least 7 days, be considered neurologic deterioration, unless attributable to co-morbid events or changes in corticosteroid dose.
- d. Failure to return for evaluation due to death or deteriorating condition.

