5.4 End of Treatment Visit

For patients who come off study for toxicity or withdrawal of consent, tumor imaging is at the judgment of the investigator, suggested every 8-12 weeks in the appropriate setting after termination of the study therapy.

If patients come off treatment for progression of disease (Arm B only), intolerance, or withdrawal, they will be seen for assessments of efficacy and safety.

Patients will have repeat safety labs, a clinical examination, weight and KPS assessments, and concurrent medications within 30 days of the last infusion.

If tumor assessments are not done within 4 weeks, these will be obtained within the next 2 weeks after the End of Treatment Visit. After the end of treatment, each subject will be followed for 30 days for adverse event monitoring and 100 days for serious adverse event reporting. Participants removed from protocol therapy for unacceptable adverse events (Section 7) will be followed until resolution or stabilization of the adverse event.

Subjects who discontinue for reasons other than progressive disease will have post-treatment

follow-up for disease status until disease progression, initiating a non-study cancer treatment, withdrawing consent or becoming lost to follow-up. Subjects will be followed for survival every 2-3 months for a minimum of 1 year, or indefinitely until death or loss to follow-up.

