13.2 Definitions

Evaluable: All study-eligible patients who receive at least one infusion of nivolumab will be considered *evaluable for safety and toxicity*. To be *evaluable for efficacy*, patients must be study eligible, receive at least one cycle (6 weeks) of immunotherapy and complete initial disease assessment at ≥ 6 weeks after starting therapy.

Exclusions: Any patient who is enrolled on study, but does not receive any component of study treatment, will be excluded from all efficacy analyses. Any patient who initiates treatment and is later found to be ineligible for study (e.g., protocol violation) will be withdrawn from study but will be followed for disease progression, toxicity and survival. The experience of such patients will be characterized separately from that of evaluable patients. Reasons for exclusion of enrolled patients from the analysis set for efficacy, or for safety, will be characterized.

Overall response rate (ORR): Overall response rate is the proportion of patients whose best overall response per modified iRANO criteria or standard RANO criteria is complete (CR) or partial (PR) after at least 6 weeks from start of therapy. iRANO additionally requires best overall response of CR or PR to be sustained, that is, confirmed by a second assessment at \geq 4 weeks later. Patients who clinically progress before the initial radiographic assessment after 1 cycle (6 weeks) will be considered nonresponders.

Progression-free survival (PFS): PFS will be measured from the start date of treatment until

documented evidence of disease progression, clinical progression or death from any cause, after at least 8 weeks from start of therapy. Radiographic progression should be confirmed by a second assessment at \geq 4 weeks later. For patients who remain alive without progression, follow up time will be censored at the date of last assessment.

Overall survival (OS): Survival will be measured from the start date of treatment to the date of death from any cause or last contact (censored observations).

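### A growth scan with no confirming scan is reclassified as stable disease, so clinically stable patients with size-only growth who are not re-imaged are censored at that scan or counted only at death, and PFS reads too high

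*Combined protocol and SAP*

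**What the plan says.** Section 11.3.3a defines progression by size as an increase of more than 25% in the sum of products of enhancing lesions. It then adds: "In the absence of a confirming scan at least 4 weeks later, this scan will be considered only stable disease". The same sentence closes the size criterion for complete response (11.3.1a) and for partial response (11.3.2a).

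The other three routes to progression in 11.3.3 carry no such fallback:
- (b) "Any new enhancing measurable lesion"
- (c) "Clear clinical deterioration not attributable to other causes apart from the tumor"
- (d) "Failure to return for evaluation due to death or deteriorating condition"

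Section 13.2 defines the PFS event as "documented evidence of disease progression, clinical progression or death from any cause, after at least 8 weeks from start of therapy". It adds "Radiographic progression should be confirmed by a second assessment" at least 4 weeks later, and then: "For patients who remain alive without progression, follow up time will be censored at the date of last assessment". It does not say which scan dates the event or what happens if the second assessment never takes place. Section 13.4 plans Kaplan-Meier PFS with estimates at 6 and 12 months, and a summary of time to progression. It has no sensitivity analysis for unconfirmed progression.

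Under 5.4, patients who stop for reasons other than progression have "follow-up for disease status until disease progression, initiating a non-study cancer treatment, withdrawing consent or becoming lost to follow-up". Disease assessment can therefore end before a confirming scan is taken.

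**The concern.** The same sentence works in opposite directions in the two settings. For a response, downgrading an unconfirmed scan removes benefit that has not been proven, which is conservative. For progression, it removes growth that was observed, which flatters the treatment.

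A confirmation rule is needed here so that a later scan can overturn pseudoprogression. It need not decide in favor of stable disease when no later scan exists. A patient or physician who sees growth has a reason to change therapy before a second scan, so a missing confirmation is not a random event. Kaplan-Meier assumes that a censored patient has the same outlook as those still at risk, and this patient does not.

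At stake are median PFS, 6- and 12-month PFS, and time to progression, which loses or postpones the same dates. These are secondary endpoints, but readers of a single-treatment phase II study will compare them with other series.

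**Working it through.** **1. Who is affected.** Set against 11.3.3 and 13.2, the patient must meet all of these conditions:
- growth of more than 25% in enhancing size;
- no new enhancing measurable lesion (otherwise route b);
- no clinical deterioration (route c);
- no failure to return because of death or deterioration (route d);
- no scan at least 4 weeks later.

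Withdrawal, or a start of non-study therapy while clinically stable, fits all of them (5.4).

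**2. What 13.2 then does.** The scan counts as stable disease, so the patient is alive without progression and is censored at the last assessment, which is the growth scan itself. If death is captured in survival follow-up, the event moves to death.

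**3. Size.** The plan states no PFS assumption, so there is no figure to reproduce. The inputs are:
- scans every 6 weeks (section 11);
- a latent median of 3.6 months, the PFS in the retrospective cohort of section 2.6.2, used only as an anchor;
- exponential progression (assumption);
- f, the share of scan-detected progressions that meet every condition in step 1: 10%, 20% or 30% (assumption; the documents give none);
- a week-6 progression counts as an event (assumption, because the 8-week clause in 13.2 could be read otherwise).

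One month is 4.348 weeks. The weekly hazard is ln 2 / (3.6 × 4.348) = 0.0443. The probability of progressing within a scan interval is h = 1 − exp(−6 × 0.0443) = 0.233. If a share f is censored at the growth scan, the Kaplan-Meier factor per scan is s = 1 − (1 − f)h. Four scans (week 24) fall before 6 months and eight (week 48) before 12 months.

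| f | s | 6-month PFS = s⁴ | 12-month PFS = s⁸ | First scan with s^k ≤ 0.5 |
|---|---|---|---|---|
| 0 | 0.767 | 34.6% | 11.9% | week 18 (4.1 months) |
| 10% | 0.790 | 38.9% | 15.2% | week 18 (4.1 months) |
| 20% | 0.813 | 43.8% | 19.2% | week 24 (5.5 months) |
| 30% | 0.837 | 49.0% | 24.0% | week 24 (5.5 months) |

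This closed form ignores deaths between progression and the next scan, which remain events whatever f is. A simulation of 20,000 patients includes them, with an assumed median survival of 4 months after progression. The affected patients were censored, dated at death, or split evenly between the two.

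| f | 6-month PFS | 12-month PFS | Median (months) |
|---|---|---|---|
| 0 | 33.8–34.5% | 11.1–11.7% | 4.1 |
| 10% | 38.1–38.2% | 14.3–14.5% | 4.1 |
| 20% | 41.6–42.7% | 16.3–18.4% | about 5.5 |
| 30% | 45.5–47.4% | 18.9–22.2% | about 5.5 |

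The rise in 6-month PFS is about 4 points per 10% unconfirmed, whether affected patients are censored or dated at death. The median moves only in steps of one scan interval.

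**4. Disease control.** Clinical benefit in 13.1 needs stable disease beyond 12 weeks.
- A patient who leaves after week-6 growth cannot reach it. Only the best response changes, to stable disease, in about 2%, 4% and 6% of all patients at f = 10%, 20% and 30%.
- First growth at week 18 or later, after stable scans, meets it under either classification.
- Only first growth near week 12 can change it, by at most about 1.5, 3 and 5 points, and only if the scan falls after 12 weeks within its ±7-day window.

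**5. ORR.** An unconfirmed progression becomes stable disease and never a response, so the primary endpoint and the two-stage rule do not change.

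**The case against.** The case on the other side is that the plan makes a missing second scan uncommon. Scans are 6-weekly, so the next routine scan is itself a confirming scan. Sections 5.3 and 11.1 ask for repeat imaging after suspected progression. The calendar in section 10 lists imaging at the End of Treatment visit. Arm A patients who progress on nivolumab alone move to added ipilimumab on study and would normally be re-imaged. Confirmation is deliberate, given the pseudoprogression provisions in 1.1, 5.3 and 5.8. PFS is secondary and descriptive, with no test attached.

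Most of this stands, and it makes the affected group small. It does not close the gap. An instruction to re-image is not a rule for a patient who is not re-imaged. Section 5.4 asks for end-of-treatment tumor assessment only when none was done within 4 weeks, so a recent growth scan can satisfy it. An end-of-treatment scan may also fall less than 4 weeks after the first. Section 5.8 ties stopping once to radiographic progression and once to confirmed radiographic progression, so leaving after one scan is possible.

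Two stronger readings are tempting. A reader might infer that everyone who leaves after a first progression scan is lost as an event. Routes b, c and d, and the inclusion of clinical progression and death in 13.2, rule that out. A reader might also infer that disease control in general is inflated. For the plan's own clinical benefit endpoint the effect is confined to scans near week 12.

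**Conclusion.** The point holds in a narrow form. Under the text as written, a clinically stable patient with size-only growth and no later scan is censored at the growth scan or counted only at death. The censoring is informative, and its effect on PFS is upward. Time to progression uses the same classification, so it loses these dates or takes them too late.

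The direction follows from the documents. The size does not, because the unconfirmed fraction is not given. At 10% to 30% of scan-detected progressions, and with the exponential, 3.6-month and 4-month assumptions above, 6-month PFS reads about 38% to 47% instead of about 34%. The median is unchanged at 10% and one scan interval later at 20% to 30%. Clinical benefit changes marginally and ORR not at all. This should be corrected, but it does not threaten the primary analysis.

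**What to change.** In 13.2, for PFS and time to progression only, state:
- Radiographic progression is dated at the first scan that meets the criterion.
- It is overturned only if a scan at least 4 weeks later does not confirm it.
- If no later scan is obtained, for any reason, the first scan stands as the event.

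Report PFS under the 11.3.3a stable-disease handling as a sensitivity analysis, with the number of patients whose classification differs. Keep the stable-disease downgrade for unconfirmed complete and partial responses. Leave the rules on continuing treatment as they are, since the same definition of progression bears on stopping and on the Arm A switch.

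Two conflicts also need to be reconciled by the sponsor. Section 11.3.3a asks for growth sustained for at least 8 weeks and also for a confirming scan at least 4 weeks later. Section 5.8 refers both to radiographic progression and to confirmed radiographic progression.

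The cost is a wording change with no new data. The downside is that a few pseudoprogressions that were never re-imaged will count as events, so PFS may read slightly lower.

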11.1 Definitions

Evaluable for Objective Response Only those patients with measurable disease present at baseline will be enrolled on study.

Only patients who received at least one cycle (6 weeks) of therapy and response assessment with brain MRI or CT at least 6 weeks from the first dose will be considered evaluable for overall survival or disease progression. Patients who discontinue therapy for reasons other than progression prior to response assessment will not be evaluable for survival and will be replaced.

Only patients with measurable disease present at baseline, completing at least one cycle (6 weeks) of therapy, and disease re-evaluated radiographically will be considered evaluable for partial or complete response.

Any patient who initiates treatment and is later found to be ineligible for study (e.g., protocol violation) will be withdrawn from study but will be followed for disease progression, toxicity and survival. The experience of such patients will be characterized separately from that of evaluable patients. Reasons for exclusion of enrolled patients from the analysis set for efficacy, or for safety, will be characterized.

Evaluable Non-Target Disease Response

Patients with lesions present at baseline that are evaluable but do not meet the definitions of measurable disease, have received at least one cycle (6 weeks) of therapy, and have had their disease re-evaluated will be considered evaluable for non-target disease. The response assessment is based on the presence, absence, or unequivocal progression.

All patients who have received at least one dose infusion of nivolumab and/or initiate TTFields therapy are evaluable for safety and toxicity.

Disease Parameters

For the purposes of this study, patients will be evaluated for response approximately every 6 weeks of therapy starting from the first dose for the initial 24 months, thereafter approximately every 8 weeks. In addition to baseline scans, confirmatory scans will be obtained at \geq 4 weeks following initial documentation of objective response or disease progression.

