11.3.4 Stable disease (SD)

All of the following criteria must be met:

- a. Does not qualify for CR, PR, or progression.
- b. All measurable and non-measurable sites must be assessed using the same techniques as baseline.
- c. Stable clinically.

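### The progression criteria in 11.3.3 give no rule for growth of existing non-measurable disease, so on the literal list a clinically stable patient with such growth is scored as stable disease

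*Combined protocol and SAP*

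**What the plan says.** **Progressive disease (11.3.3).** Any one of four criteria suffices:

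- a: ">25% increase in sum of the products of perpendicular diameters of enhancing" lesions, with a confirming scan.
- b: "Any new enhancing measurable lesion".
- c: "Clear clinical deterioration not attributable to other causes apart from the tumor".
- d: not returning for evaluation because of death or decline.

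**Stable disease (11.3.4).** The first condition is "Does not qualify for CR, PR, or progression". The others are assessment of all sites by the baseline technique and clinical stability.

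**Partial response (11.3.2).** Item b requires "No progression of non-measurable disease". Item c rules out a new lesion of any kind, with no measurability limit.

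**Non-target disease (11.1).** For lesions that are evaluable but not measurable: "The response assessment is based on the presence, absence, or unequivocal progression".

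**Which lesions are followed (11.2).** "If there are too many measurable lesions to measure at each evaluation, the investigator must choose the largest two to be followed". For the others: "The remaining lesions will be considered non-measureable for the purpose of objective response determination".

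**Best response (11.5).** A participant without measurable disease can reach only SD or PD.

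**Endpoints.** In 13.2, PFS ends at documented disease progression, clinical progression or death. In 13.1, clinical benefit is ORR plus stable disease lasting more than 12 weeks.

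**The concern.** The protocol has non-measurable lesions assessed, and their growth can deny a patient a partial response. The list that defines progression does not use that information. If SD is whatever remains, growth that the protocol elsewhere recognises as progression counts as disease control until another trigger is met.

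PFS, time to progression, duration of response and clinical benefit all depend on when PD is declared. In an open-label trial with investigator-read scans, there is a second risk: two sites could score the same scan differently, one from 11.1 and the other from 11.3.3.

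**Working it through.** The plan states no figure on this point, so the check is mainly a comparison of passages.

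**Step 1. Take a clinically stable patient whose followed lesions are unchanged, with no new lesion and unequivocal growth of an existing non-measurable enhancing lesion. Go through 11.3.3.**

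- Criterion a needs a sum of products of perpendicular diameters. Under 11.2, non-measurable disease includes lesions measurable in one dimension only, lesions with unclear margins and lesions under 1 cm. Such lesions do not reliably contribute to that sum. Not met.
- Criterion b concerns new, measurable lesions. Not met.
- Criterion c needs clinical deterioration. Not met.
- Criterion d needs failure to return. Not met.

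**Step 2. Apply the other categories.** Complete response requires all enhancing disease, measurable or not, to disappear: not met. Partial response fails on item b. With all sites assessed and the patient clinically stable, 11.3.4 gives SD.

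**Step 3. Compare with the rest of the protocol.** In 11.1 the same finding is unequivocal progression of non-target disease, but no passage maps that result to overall PD or to a PFS event. Section 11.5 accepts PD in participants without measurable disease; 11.3.3 lets them reach it through a new measurable lesion, clinical decline or failure to return, but has no rule for growth of what they already have.

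**Step 4. Direction.** Omitting a trigger can postpone PD or leave it unrecorded; it cannot bring PD forward. PFS, time to progression and the share with SD beyond 12 weeks therefore move up. So does response duration, because 11.5 runs a sustained response until tumour progression.

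**Step 5. Primary endpoint.** At any scan showing such growth, item b blocks partial response and the disappearance requirement blocks complete response. Scoring the patient SD instead of PD adds no responder.

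**Step 6. Scale, by assumption only.** In an arm of 30, one patient is 1/30 = 3.3 percentage points of a 6-month PFS or clinical benefit rate. Let t be the true rate free of progression and q the share of true progressors labelled SD. Extra patients = 30 × (1 − t) × q. Neither t nor q is given for this trial; t is taken as 0.21 to 0.40 and q as 2% to 20%.

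| q | t = 0.21 | t = 0.40 |
|---|---|---|
| 2% | 30 × 0.79 × 0.02 = 0.47 | 30 × 0.60 × 0.02 = 0.36 |
| 5% | 1.19 | 0.90 |
| 10% | 2.37 | 1.80 |
| 20% | 4.74 | 3.60 |

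The result ranges from under half a patient to almost five. It is set by q, on which the documents are silent.

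**The case against.** The strongest reply is that the protocol is not silent. Section 11.1 names the category, 11.3 presents itself as a summary of RANO, and the PFS definition in 13.2 does not cite the 11.3.3 list. A careful site could score the patient PD. This stands in part: SD is the literal outcome, not a certain one. But 11.3.3 is the only list of PD criteria in the document, and 11.3 says RANO applies as summarised there.

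A reader might infer more from the text than it supports:

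- *That every lesion beyond the largest two drops out of progression.* The rule in 11.2 applies only when lesions are too many to measure, and it reclassifies them for objective response. Criterion a refers to enhancing lesions, whereas partial response refers to measurable ones, so a site may keep unfollowed measurable lesions in the PD sum. The gap for lesions that are non-measurable in their own right does not depend on this.
- *That median PFS is overstated by a known amount.* One patient's delay to a later scan does not move a cohort median by that delay, and the number of such patients is unknown.
- *That the primary result is affected.* Steps 2 and 5 of the working show that it is not.
- *That a new lesion of any size should be PD.* The protocol guards repeatedly against pseudoprogression, and limiting criterion b to measurable lesions may be deliberate. That is a design choice.

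The affected group is also narrow. All patients must have measurable disease at entry, which limits the weight of the sentence in 11.5, and clinical decline is PD whichever lesion grows. These facts bear on size; they do not remove the contradiction. The affected endpoints are secondary, with no stopping rule attached.

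**Conclusion.** The point holds as an unreconciled definition with a one-sided effect. Applied literally, 11.3.3 and 11.3.4 make a clinically stable patient with unequivocal growth of existing non-measurable enhancing disease SD, against 11.1 and 11.3.2 item b. PFS, time to progression, response duration and clinical benefit are then biased upward; primary ORR is not inflated.

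The conclusion assumes that sites score from the 11.3.3 list. If some use the 11.1 category instead, the bias shrinks but scoring becomes inconsistent. The size cannot be derived from the documents: the table is an illustration over assumed values. This should be corrected because it touches several reported endpoints and the assessments are already required, but it does not threaten the primary analysis.

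**What to change.** For endpoint scoring, add a criterion to 11.3.3: unequivocal progression of non-measurable enhancing disease, as named in 11.1 and including any measurable lesions not followed under 11.2, counts as PD, subject to the same confirmation scan as criterion a. State in 13.1 and 13.2 that this list defines PD for clinical benefit and PFS.

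Two reconciliations belong with it:

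- Partial response item c excludes any new lesion, while PD item b counts only measurable ones. The sponsor should say how a new non-measurable lesion is scored.
- Progression also governs treatment in 1.1, 5.1 and 5.8. The sponsor should reconcile those passages with the revised endpoint definition. No treatment rule is proposed here.

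The cost is one added criterion and the cross-references, with no new scans beyond the confirmation already required when progression is suspected. PFS and clinical benefit may become slightly less favourable.
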